The Visual analogue Scale (VAS) scar scoring system was defined and validated by Duncan et al. in 2006. This scale consists of a 10-cm line representing scar quality, with 0 representing normal skin and 10 indicating a poor scar. The assessor places a mark along the line to represent the appearance of the scar. This mark is then translated into a score by measuring its position on the 10-cm line to one decimal place.

Visual Analogue Scale (VAS) scar scoring system

The improvement in the appearance of the scar will be evaluated using a paired t-test for the mean difference. The paired t-test will be used to compare the treated side and untreated (control) side of the scar to determine if there is a statistically significant improvement in the average difference of Visual Analogue Scale (VAS) measurements (difference determined by VAS measurements pre- and post-treatment). Efficacy will be determined by at least 2 out of 3 blinded physician evaluators, comparing baseline photographs to photographs taken approximately 90 days after the last treatment.

Subject Feedback (patient perception) Endpoint - Patient satisfaction will be determined by evaluating scores on a subject satisfaction survey to be completed approximately 90 days after the last treatment. Subjects will indicate on the survey whether they saw improvement in the areas treated. Baseline and 90 day post-treatment photographs will be made available for viewing by the patient for their assessment. Subjects will have access to a full length mirror in a room lit by natural light. T-tests will be used to determine if on average patients had a good experience and saw improvement in the appearance of the scar while being treated by evaluating ratings from the Self-Assessed Scar Improvement Scale and the Subject Global Aesthetic Improvement Scale. For the Self Assessed Scar Improvement Scale, ratings of 1 and

greater (1=1%-25% improvement, 2=26%-50% improvement, 3=51%-75% improvement, and 4=76%-100% improvement) indicate that patients were satisfied with the treatment. For the Subject Global Aesthetic Improvement Score, ratings of 3 and lower (1=very much improved, 2=much improved, 3=improved) indicate that patients were satisfied with the treatment.

The Subject Satisfaction Survey is a 6-point scale (1-6) describing an overall assessment as follows:

Rating	Description
6	Very satisfied
5	Satisfied
4	Somewhat satisfied
3	Somewhat dissatisfied
2	Dissatisfied
1	Very dissatisfied

Safety Endpoint

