- a. General – a digital photography system shall be used to take photographs. The system set up and the patient positioning shall be standardized across the population for both baseline and post treatment digital pictures. To the greatest extent possible the photographic equipment shall be fixed in a single location and not be moved or taken down during the trial. If the photography equipment must be moved, the exact location and orientation shall be recorded to permit the photography equipment to be reinstalled in a standardized orientation for baseline and treatment photographs. For each photograph taken the SkinStylus® settings, number and duration of treatments to the location shall be recorded in the CRF.

- b. Baseline – prior to SkinStylus® treatment a digital picture of each treatment location shall be taken and a description of the hypertrophic scar shall be recorded in the CRF. The description should include skin assessment using the Fitzpatrick scale (see table on page 16).
- c. 90 days following the final treatment a digital photograph using an identical technique to that used in baseline photograph shall be taken and used for evaluation
- d. When taking baseline and post treatment digital pictures if the treatment location is in close proximity to the patient's face, the patient:
 - o Shall not wear any makeup or skin care products in or around the treatment areas. Make-up includes any type of lipstick, mascara, eyeliner, foundation or any other article which alters the nature appearance of the skin in and around the treatment areas.
 - o Patients shall not wear any jewelry in or around the treatment areas. This includes earrings; piercings; necklaces or other article which may obscure the digital photograph.
 - o Patients shall not wear glasses.
 - o The patient's hair shall be approximated identically in both baseline and post treatment photographs. The hair should be held up and away from the treatment areas using hairpins. Hairbands should be avoided. Preferably, the patient 's hair shall be covered using a white hair cover as is used in clean rooms
 - o Patients shall be encouraged to make no facial expression to avoid altering the natural appearance of the treatment area.
 - o The patient's eyes should be closed for each photograph.
- e. When taking baseline and post treatment digital pictures if the treatment location is not in close proximity to the patient's face, the patient:

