- b. The technician administering the treatment shall further clean the treatment areas, if necessary.
- c. The hypertrophic scar to be treated shall be divided into two equal segments and the technician shall randomly choose one half to be treated.

- d. The technician shall describe in the CRF, which half of the scar was treated.
- e. Subsequent treatments shall only treat the same half of the scar that was initially designated the treatment side.
- f. If the scar is to be locally anesthetized, the entire scar (both halves) are to be anesthetized.
- g. A proprietary glide serum, EstheCeuticals® HA-Cu Serum, shall be applied prior to treatment and again as necessary. The purpose of the serum is to act as a glide and no therapeutic effect is known or anticipated. This serum has been used in several hundred microneedling treatments without any incidence of adverse events.
- h. The depth settings and clinical endpoints shall be established by the PI.
- i. Each participant shall receive three SkinStylus treatments .
- j. Each participant shall receive one treatment using each of the three different array configurations. The order in which each is used shall be randomized at intake but a different array configuration must be used in each of the three treatments.
- k. The treatments shall be not less than 12 days or more than 14 days apart.
- l. The treatments shall consist of 2 to 3 passes at the targeted area over a period of 15-30 minutes.
- m. While the technician may adjust the treatment settings, the treatment settings shall remain within the range specified by the PI, usually 2.5mm depth.
- n. At the conclusion of treatment the technician completes the CRF as stipulated.
- o. 90 days following the final treatment the post treatment photograph shall be taken and recorded in the CRF. There may be other photographs taken periodically during the trial in addition to the dermal spectroscope readings taken.
- p. 180 days following the initial treatment the patients shall be evaluated to provided objective evidence of what adverse incidents, as previously defined, may have occurred.

D. Determination of Results

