A panel of 3 physicians who are either dermatologists or plastic surgeons (and not affiliated with the trial or Esthetic Education LLC) shall review the baseline and post treatment photographs and score each them using the VAS scar score on page 7. A successful outcome on the primary endpoint (efficacy) shall be determined to a statistically significant improvement when comparing the score determined for the 90 day post final treatment photographs to the score determined at baseline.

A successful outcome on secondary endpoint (patient feedback) shall be determined by the evaluation of the Subject Satisfaction Survey on page 7.

The evaluation of the third endpoint (safety) shall be determined by the relative lack of adverse incidents as previously defined above.

E. Statistical Analysis for the SkinStylus® Clinical Study

The sample size for this study consisted of 30 subjects with assessable data. Performance will be evaluated by the (VAS) visual analogue scale scar score as described above from SkinStylus® treated sites and control sites at approximately 90 days after the final treatment.

The VAS scar scoring system was defined and validated by Duncan et al. in 2006. This scale consists of a 10-cm line representing scar quality, with 0 representing normal skin and 10 indicating a poor scar. The assessor places a mark along the line to represent the appearance of the scar. This mark is then translated into a score by measuring its position on the 10-cm line to one decimal place.

Measurements:

- a) *Primary Endpoint:* A statistically significant improvement between the measurements taken at baseline and two weeks following the end of the treatment, on the VAS Scar Scale. The scores are determined based on a panel of three independent physicians (dermatologist and/or plastic surgeons).
- b) *Second Endpoint:* The patient surveys shall be tabulated and reported. It is anticipated the patients shall have a good experience while being treated by the SkinStylus for scar revision.
- c) *Third Endpoint:* - The tertiary endpoint is the relative absence of adverse incidents as previously defined.

Prior data indicate that the standard deviation of the paired differences in visual analogue scale scores is not expected to exceed 1.46.

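### The primary analysis needs a VAS score for each half of the scar at baseline and at 90 days, but the photograph, scoring and success rules do not carry this through

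*Combined protocol and SAP*

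**What the plan says.** **The analysis is at the level of the half.** Under Efficacy (primary) Endpoint, "The paired t-test will be used to compare the treated side and untreated (control) side of the scar", with each side's value given as a "difference determined by VAS measurements pre- and post-treatment". Section E says that performance is judged on VAS scores "from SkinStylus® treated sites and control sites at approximately 90 days after the final treatment".

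**The procedures are at the level of the scar or the photograph.**
- C.9.b: "prior to SkinStylus® treatment a digital picture of each treatment location shall be taken". C.9.c asks for one 90-day photograph by the same technique as at baseline.
- VAS definition (Efficacy Endpoint, repeated in Section E): "The assessor places a mark along the line to represent the appearance of the scar".
- Section D: the three physicians "shall review the baseline and post treatment photographs and score each them using the VAS scar score on page 7". Success is then a significant improvement of the 90-day score over the baseline score. The control half is not mentioned.
- C.12.c to e: the scar is split into equal halves, one is chosen at random, and later sessions stay on that half. For the record, "The technician shall describe in the CRF, which half of the scar was treated". C.11.c makes the CRF the sole source record.

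**The concern.** The quantity to be tested exists only if someone scores the treated half and the control half separately, at both times. The instructions to the photographer, the technician and the evaluators never say so. A site that follows C.9 and Section D to the letter could end with two whole-scar scores per patient and evaluator. Those mix treated and untreated tissue and hold no within-patient control. Or the evaluators could divide the scar by eye, at a line that need not be where needling stopped.

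Part of the loss cannot be repaired later. If the control half is outside the baseline picture, its pre-treatment appearance cannot be recovered by photograph once treatment has begun, and that patient has no control change.

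**Working it through.** **1. Scores needed.** For each patient and evaluator the contrast is (T90 − T0) − (C90 − C0), where T and C are the treated and control halves and 0 and 90 are baseline and 90 days. That is 2 halves × 2 times = 4 scores.

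**2. Scores specified.**
- *Images:* C.9.b and c name a treatment location. This may mean the whole scar or only the part to be needled, and the control half is not named.
- *Scores per image:* not stated. The scale is described for the scar, and Section D gives no number.
- *Dividing line:* C.12.c puts it at the midpoint. No item says how the midpoint is measured, marked, found again at treatments 2 and 3, or shown to the evaluators.
- *Success rule:* the Efficacy Endpoint compares halves, and Section D compares times. Item a) under Measurements in Section E also compares times only.

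The literal minimum is therefore 2 scores, T and C combined at each time.

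**3. What the plan's power statement implies.** Inputs from Section E: N = 30, SD of paired differences at most 1.46, one-tailed alpha 0.05, power at least 80%. No effect size is given, so the 80% cannot be reproduced, only inverted. I take 1.46 to be the SD of the treated-minus-control difference in change, which the plan does not state.
- Normal approximation: 1.46 × (1.645 + 0.842) / √30 = 0.66.
- Noncentral t with 29 degrees of freedom: 0.68 VAS units.

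**4. Hypothetical A: one score for the whole scar.** Assume that the score is the mean of the two halves. Let c be the change common to both halves and δ the treatment effect, both counted as improvement. The whole-scar change is then [(c + δ) + c] / 2 = c + δ/2.
- With c = 0, δ = 0.68 and the same SD, the test sees 0.68 / 2 = 0.34, and power is about 34%.
- With δ = 0 and c above 0, the test estimates c. A pre/post success rule could then be met without any treatment effect.

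**5. Hypothetical B: halves divided by eye.** Assume that the score averages linearly along the scar and that a fraction f of the scored control half was in fact treated. The contrast becomes (1 − f)δ, with f = overrun / half-length. Scar lengths and overruns are assumed, as the documents give neither.
- 10 cm scar, 0.5 cm overrun: f = 0.5/5 = 10%.
- 10 cm scar, 1 cm overrun: f = 1/5 = 20%.
- 5 cm scar, 0.5 cm overrun: f = 0.5/2.5 = 20%.

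At δ = 0.68, a 10% loss leaves 0.612 (power about 72%) and a 20% loss leaves 0.544 (about 64%).

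**The case against.** A reader might infer that the primary parameter cannot be derived at all, or that the boundary between the halves is never fixed. The documents support neither.

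- Section E names treated and control sites, and the Efficacy Endpoint names both sides and both times. The four quantities are intended.
- C.9.b can fairly be read as the whole scar. The same item asks for a description of the scar, not of a half. C.9.d and e use the same term for a body site. The picture precedes treatment and may precede the choice of half. Eligibility requires a scar that can be seen as two halves.
- The VAS text explains how to mark the line. It does not limit an evaluator to one mark, and one photograph can carry two scores.
- Equal halves put the boundary at the midpoint, C.12.e keeps the same half throughout, and C.9.a standardizes camera and positioning. Needling past the midpoint would itself depart from C.12.e.
- Adjoining halves belong to any split-scar design and are not an error.
- Dividing the scar wrongly by eye shrinks the contrast and does not by itself create a false benefit.

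All of this stands, and it limits the point to what the procedures leave unspecified. It does not remove the point. No item tells the evaluators to score each half, requires the control half in frame, or records a landmark. The argument about shrinkage also does not cover whole-scar scoring, where the control is lost and a common change counts as success.

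**Conclusion.** The point holds as a gap between analysis and procedure. Half-level scoring is implied by the primary analysis but is not written into the photograph, scoring, boundary or success rules. The likely intention is clear, yet literal compliance with C.9 and Section D can lose the control contrast or dilute it.

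The size is unknown. The 10 to 20% dilution and the power figures are hypothetical. They rest on assumed scar lengths and overruns, on linear averaging of an overall appearance score, and on reading 1.46 as the SD of the treated-minus-control difference. The conclusion does not depend on them. It rests on the count of scores needed against scores specified, and on the fact that a missing baseline image of the control half cannot be replaced. The wording should be settled before the first baseline photograph.

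**What to change.** - **C.9.b and c:** require baseline and 90-day photographs that show the whole scar, both halves, with a ruler in the picture.
- **C.12.c and d:** record the midpoint in the CRF as a measured distance from a fixed landmark, and reuse it at each treatment and at 90 days.
- **Section D, scoring:** split each photograph at that line. Have each evaluator give a separate VAS score to each half at each time, without being told which half was treated.
- **Section D, success rule:** state it as the treated-minus-control difference in change, as under Efficacy (primary) Endpoint, and align item a) under Measurements in Section E.
- **Optional:** leave a narrow strip at the junction unscored, with its width stated in advance.

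The cost is protocol wording, a ruler and minor image preparation. Scoring takes 4 scores per patient and evaluator: 30 × 4 × 3 = 360 in all, against 30 × 2 × 3 = 180 if each photograph were scored once. Sample size, alpha and treatment are unchanged.

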The trial shall be under the supervision of a duly accredited Institutional Review Board or equivalent ethics oversight committee. The SkinStylus® and this trial is considered a Non-Significant Risk (NSR) as the device is being used entirely within its foreign agency cleared performance specification.

The trial shall be monitored at planned and at unannounced intervals by a Registered Nurse who has appropriate training in the conduct of medical research. The RN Monitor shall ensure the trial is conducted according to the requirements of the approved protocol. In addition to examining the Case Report Forms (CRF) for each participant the RN Monitor shall review the digital photographs taken and will report to the PI any instance where an injury may have occurred.

The PI and all sub-PI's shall be appropriately trained in the *Protection of Human Subjects* as provided by the National Institute of Health or equivalent body.

C. Trial Design

1. The SkinStylus has been designated as a non-significant risk and therefore will be granted an Investigational Device Exemption (IDE). There are no meaningful

changes to the SkinStylus® instructions for use and specifically no new risks will be introduced.

2. There are three endpoints under investigation. The primary endpoint is a statistically significantly improvement using the VAS scale on page 7. The secondary endpoint is patient feedback by the Subject Satisfaction Survey on page 7. The third endpoint is safety related and is the absence of adverse incidents as previously defined.
3. The trial shall be blinded and bias minimized in that three (3) physicians who are either dermatologists or plastic surgeons (and not affiliated with the trial or Esthetic Education LLC) shall review the baseline and treatment photographs and score them using the VAS scale (see page 7).
4. Inclusion Criteria - patients age 23 years or older as described on page 6. The subjects shall all be volunteers. Subjects shall not be hand picked or otherwise manipulated or shown favor. There will be some effort expended to ensure reasonable representations of both sexes and of all Fitzpatrick Skin Types as shown below:

Type	Score	Description
I	0-6	Skin always burns; never tans. (Pale peach, blond, or red hair, blue eyes, freckles)
II	7-13	Skin usually burns, tans minimally (peach; fair; blond or red hair; blue, green, or hazel eyes)
III	14-20	Skin sometimes mild burn, tans uniformly (light brown; fair with any hair or eye color)

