 - o Shall not wear any makeup or skin care products in or around the treatment areas. Make-up includes any type of cosmetic, temporary tattoo or any other article which alters the nature appearance of the skin in and around the treatment areas.
 - o Patients shall not wear any jewelry in or around the treatment areas. This includes piercings; necklaces or belts or other article which may obscure the digital photograph.

- The photograph shall be taken with the patient standing in a completely relaxed fashion.
- The patient's hair shall be approximated identically in both baseline and post treatment photographs. The hair should be held up and away from the treatment areas using hairpins. Hairbands should be avoided. Preferably, the patient 's hair shall be covered using a white hair cover as is used in clean rooms.

NOTE: Any personal identifying features shall be obscured electronically in order to avoid any twisting or other unintentional distortions within the photograph.

10. Dermal Spectroscope readings.

- a. General – a specialized dermal spectroscope may be used to measure the color of the skin in the treatment area. This device painlessly scans the skin and provides a melanin and redness reading in the form of an integer.
- b. For each set of data captured by the dermal spectroscope, the SkinStylus® settings, number and duration of treatments to the location shall be recorded in the CRF.
- c. Baseline – prior to SkinStylus® treatment, data readings from the dermal spectroscope of each treatment location may be taken and a description of the atrophic scar treatment areas shall be recorded in the CRF.

11. Records

- a. The CRF shall be considered the principal record of the study.
- b. The CRF shall contain all records of treatment as well as the photographs taken.
- c. The CRF shall be the only record used for source data.
- d. In consideration of HIPAA requirements, the CRF shall identify patients only by code using the first three letters of the device name and a numerical designation. For example – O17-1; O17-2, etc.
- e. The Study Coordinator ([name]) shall maintain a key which can be used to identify a particular patient, if necessary. The Registered Nurse Monitor ([name] RN) shall have access to the key upon request.

12. Sequence of Treatment

- a. The patient shall wash the treatment area to remove dirt, cosmetics and other impurities from the treatment area.

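### C.12.c leaves the choice of treated scar half to the treating technician, with no sequence, no concealment and no record of how the choice was made

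*Combined protocol and SAP*

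**What the plan says.** Section C.12 (Sequence of Treatment) divides the scar into two equal segments, and then "the technician shall randomly choose one half to be treated" (C.12.c). The preceding item describes this person's role: "The technician administering the treatment shall further clean the treatment areas, if necessary" (C.12.b). The record required is the outcome of the choice: "The technician shall describe in the CRF, which half of the scar was treated" (C.12.d). Under C.12.e the same half is treated at every later session, so one choice fixes the comparison for that participant.

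The protocol's other randomization concerns the three needle arrays: "The order in which each is used shall be randomized at intake" (C.12.j). It does not decide which half is treated, and its method is not described either.

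The analysis that depends on the choice is in the Efficacy (primary) Endpoint section: "The paired t-test will be used to compare the treated side and untreated (control) side of the scar". What is compared is the pre-to-post difference in VAS score.

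**The concern.** The paired comparison estimates the device effect without bias only if the two halves would, on average, have changed equally without treatment. Random assignment secures that. C.12.c asks for randomness, but the only means it names is a person's own choice, made by someone who can see both halves and appears to be the one who will treat. Someone asked to pick at random without an aid can lean towards one half without intending to.

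Two kinds of leaning matter:

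- **Selection on expected natural change.** If the technician tends to pick the half that would improve more anyway, the test can be positive with no device effect.
- **Selection on expected response to the device.** If the technician tends to pick the half that looks more treatable, a real effect is exaggerated, but no false positive is created.

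A leaning the other way would hide a real effect. In none of these cases would the planned record differ from that of a properly random choice.

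**Working it through.** **1. The text, side by side.**

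| Question | Where | Answer |
|---|---|---|
| Who picks the half? | C.12.c | The technician |
| Does that person treat? | C.12.b | Indicated, yes |
| By what method? | C.12.c | Not stated beyond randomly |
| Is there a list, concealment or independent assigner? | Whole document | None specified |
| What is recorded? | C.12.d | Which half, not how it was chosen |
| Can the choice change later? | C.12.e | No |
| Does another randomization cover it? | C.12.j | No, array order only |

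The Regulatory Compliance section adds monitoring: "In addition to examining the Case Report Forms (CRF) for each participant the RN Monitor shall review the digital photographs taken". That can confirm which half was treated. It cannot confirm how the half was selected, because that is not written down.

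**2. The plan's own figure.** Section E states at least 80% power with 30 participants, one-tailed alpha 0.05, and that "the standard deviation of the paired differences in visual analogue scale scores is not expected to exceed 1.46". It gives no target difference, so the 80% cannot be reproduced forwards. Solving backwards with the noncentral t distribution (29 df, SD 1.46) gives a detectable difference of 0.68 cm. This sets the scale only; the concern does not depend on it.

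**3. Illustration of the false-positive route.** The documents give no figure for how far the halves differ in natural change or how often a technician would pick the faster one. Both are assumed here.

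- Gap in natural change between halves: 0.10 cm (assumed).
- p, the probability that the faster-improving half is picked: 0.6, 0.7 or 0.8 (assumed).
- SD of the treated-minus-control difference in change: 1.46 (the ceiling in Section E, assumed to refer to this quantity) or 1.0 (assumed).
- n = 30, one-sided 0.05, critical t (29 df) = 1.699, no device effect.

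Shift in the mean paired difference = (2p − 1) × gap. Noncentrality = shift × √30 / SD. Type I error = P(noncentral t with 29 df > 1.699).

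| p | Shift (cm) | Noncentrality, SD 1.46 | Type I error, SD 1.46 | Noncentrality, SD 1.0 | Type I error, SD 1.0 |
|---|---|---|---|---|---|
| 0.5 | 0 | 0 | 5.0% | 0 | 5.0% |
| 0.6 | 0.02 | 0.075 | 5.8% | 0.110 | 6.2% |
| 0.7 | 0.04 | 0.150 | 6.7% | 0.219 | 7.6% |
| 0.8 | 0.06 | 0.225 | 7.7% | 0.329 | 9.3% |

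If the slower-improving half were favoured instead, the shift would change sign. The error rate would fall below 5% and power would be lost.

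**The case against.** The case on the other side is substantial, and most of it stands.

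- **Randomness is required.** C.12.c says so, and a documented coin toss would satisfy it. A steered choice would breach the protocol. A reader might infer that the trial is not randomized, or that technicians will steer. The documents support neither inference, only that steering is not prevented and would not show.
- **The usual reason for concealment is weaker here.** Every participant has one half treated and one half untreated, so selective enrolment largely does not apply.
- **Other safeguards exist.** Three unaffiliated physicians score the photographs blinded (Sections C.3 and D), photography is standardized (C.9), and analysing change removes a stable difference in severity. These limit assessment bias and baseline imbalance. They do not govern which half is chosen.
- **The false-positive route is narrow.** It needs a technician who can foresee, and repeatedly picks, the half that would improve more untreated. Nothing in the documents says that halves of one scar differ in this way or that the difference can be foreseen.

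A reader might also infer a severe loss of error control. A shift of 0.20 cm would give about 18% at SD 1.46 or 28% at SD 1.0. By the formula above, that shift needs a gap in natural change of 0.20 / (2p − 1), which is 1.0, 0.50 or 0.33 cm at p = 0.6, 0.7 or 0.8. The documents do not support gaps of that size, so those rates should not be attached to this trial.

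Nor would comparing baseline VAS between halves settle the matter. It addresses initial severity, and a stable severity difference is largely removed by analysing change. It is useful to report, but does not verify the allocation.

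**Conclusion.** The concern holds in a limited form. The trial's only treated-versus-control allocation rests on an unaided choice by the person who, on the protocol's wording, gives the treatment. No sequence or concealment is specified, and no record would distinguish a random choice from a subjective one. This is more than a missing detail, because the one method named is the technician's own choice.

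The likely harm is modest, and its size and direction are unknown. Under the assumed 0.10 cm gap and 60-80% preference, type I error is about 5.8-7.7% (SD 1.46) or 6.2-9.3% (SD 1.0) against a nominal 5%. Those figures rest wholly on assumed inputs and on reading 1.46 as the SD of the difference in change. The recommendation does not depend on them. It rests on the fact that a biased choice could not reliably be detected or repaired afterwards, whereas preventing it is cheap. The change should be made, with medium confidence in its practical importance.

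**What to change.** Rewrite C.12.c so that the steps run in this order:

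1. Define the two halves (left/right or upper/lower) and take the baseline photograph. No mark on the skin may be visible in any rated photograph, since C.9 excludes articles that alter how the treatment area looks.
2. Only then reveal the treated half from a computer-generated list prepared in advance and held concealed by existing study staff who give no treatment. The Study Coordinator, who "shall maintain a key which can be used to identify a particular patient, if necessary" (C.11.e), is one candidate, provided that person does not treat; the documents do not say. The list can be prepared alongside the array-order randomization in C.12.j.
3. Record the assignment and any deviation from it in the CRF.
4. Report baseline VAS by half.

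The cost is preparing and holding one list for at least 35 participants, one CRF field and one or two protocol sentences. Sample size, visits and treatment do not change.
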